2. Components common to all trial arms

2.1 Personalized digital coupon for free HIV testing: All participants, after verifying contact information, will receive a personalized digital coupon consisting of a number (linked to their study id), and a personalized link to an arm-specific webpage listing HIV testing locations where the coupon can be used (HST and private laboratory sites). This approach has been used previously,³⁶ including in a recent feasibility pilot by our private laboratory partner, Suburban Diagnostics. The coupon will also be linked to participants' mobile numbers, and will be scanned or entered into an online system by testing staff (at HST or the private laboratory).⁵⁸ Each coupon can only be used once every 4 weeks. All participants who check in will also receive an automated message with a link for a pre- and post-test counseling video, and contact information for HST's community health worker (who can provide additional counseling and linkage-to-care/navigation for prevention and treatment, blinded to participant's study condition). These steps will help ensure confidentiality of test results and linkage of valid test results to each participant.

2.2 Informational webpage: All participants will receive a personalized link (e.g., using Bit.ly link shortened)⁵⁹ to an identical informational webpage (one webpage per arm) listing testing sites where digital coupons can be used, contact information for online peer counselors, and other MSM-specific health services offered by HST (e.g., counseling, crisis support). The use of personalized links and study arm-specific webpages will enable us to collect process data on website visits, linked to participants and outcomes.

2.3 Online peer counselors: All participants will be able to use SMT to contact HST's online peer counselors to receive support, have questions answered, or obtain referrals for linkage services. Online peer-counselors are currently supervised by HST's existing peer outreach infrastructure. For each online peer, collect communication-related process measures will be collected by downloading their message- and voice-call history to examine potential associations with study outcomes. Peers will not be informed of study hypothesis.

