2.4 Choice of HIV testing strategy: All participants will be able to use digital coupons for free testing using a strategy of their choice: (1) standard counselor-based finger-prick rapid testing at any of 3 HST testing sites across Mumbai, (2) Oraquick self-testing in a private room at any of the 3 HST testing sites, accompanied by an instructional video and brief post-test self-administered survey, or (3) 4th generation HIV antibody/antigen test at any of the 41 private laboratory sites. Those testing at HST via counselor or self-test will undergo standard pre- and post-test counseling, and those testing at the private lab will be sent pre- and post-test counseling video links. HST currently collects and verifies mobile phone numbers for clients presenting for testing (now a requirement by the health ministry), and these phone numbers will be used to determine whether any study participants received counselor-based testing at HST but forgot to show the digital coupon. Study participants will only be able to receive free self-tests at HST or test at the private lab if they show the coupon.

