2.5 Linkage-to-care based on HIV testing strategy: Specific protocols will be used for HIV-positive results, based on testing strategy. For standard counselor-based testing, HST will use current protocols for linkage and monitoring after a positive test. For private HIV self-testing at HST, a brief post-test self-administered survey will ask participants to indicate test results; we expect (based on prior non-India based studies) that the majority of those testing positive will indicate results on the post-test survey or inform the on-site HST counselor.⁶⁰⁻⁶² Post-test survey results will be visible to counselors, with participants informed of this disclosure. Once participants inform counselors of positive self-tests, participants will be linked and monitored using HST's existing protocols. We anticipate that most of those who do not immediately disclose a positive result immediately will contact HST for support. The post-test video link sent to all participants (both positive and negative) will also provide information about options for care, including free and private sector care. Finally, participants choosing private lab testing who test positive and do not contact HST within 24 hours will be contacted by the HST study healthcare worker, who will deliver results via face-to-face or live voice or video call (if face-to-face is not feasible for participant). The researchers at HST will use HST's current standard protocols to deliver positive HIV test results and provide counseling. All participants testing HIV-positive or HIV-negative will be offered linkage to care services.

3. Exit interviews. To provide insight into why **CHALO! 2.0** may or may not work to increase HIV testing and linkage-to-care and obtain data to inform intervention scale-up, the team of researchers at HST will perform phone-based exit interviews with 5-10 randomly selected participants from each of the following groups: never HIV tested, tested only once, tested multiple times, linked to HIV treatment, linked to HIV prevention care (e.g. PrEP, counseling), and not linked to care.

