8.3 Clinical outcomes data from HST computerized information system (CIS): The HST CIS contains data on all services used by clients, linked to their mobile-phone number and includes both services at HST and services at sites outside HST. The HST data manager will cross-check data weekly and merge it with the study's Avegen HM database. On-site HST services include clinic use (counseling, HIV testing, PEP, and PrEP prescribing, STI testing/treatment) and healthcare worker navigation logs (HIV treatment referral/linkage in both public centers and the few preferred private clinics, antiretroviral treatment status, and PrEP referral). In addition, the HST CIS includes data on linkage-to-care and outcomes from public ART centers for all referred clients, because HST is an official voluntary testing-counseling center under the Indian Health Ministry. Finally, because of reporting requirements and the mandate to provide choices to clients, HST refers to a small number of vetted MSM-competent private HIV treatment providers with whom there are linkage agreements for HST to obtain client follow-up and ART use data (confirmed with clients themselves) and entered the data into HST's CIS. For study participants who self-report linkage-to-care anywhere outside HST or HST's partners, questions about care status (ART treatment, counseling, STI testing, PrEP use) and request permission (via an emailed statement) will be asked to have study staff from HST verify the information. Due to privacy concerns, not all participants may be willing to share this level of information.

8.4 Process measures: Process measure data will include messaging frequency, online peer counselor interactions, and study website visits. Whatsapp Business Analytics will be used to assess whether messages were received and

Anticipated, perceived, and community HIV stigma	India HIV Stigma Scale ^{75,76}	●	●	●	●	●
MSM internalized and community stigma	MSM Stigma Scale ⁷⁷	●	●	●	●	●
Identity disclosure	Sexual Identity and Presentation ²³	●	●	●	●	●
HIV knowledge, risk perception	HIV Knowledge Scale ⁷⁸	●	●	●		
HIV testing attitudes, intentions	Attitudes Towards Testing Scale ^{79,80}	●	●	●		
Self-efficacy (testing, coping, care linkage)	Self-Efficacy scales ^{80,81}	●	●	●		
Knowledge of free MSM-sensitive HIV testing sites	Zero Meters Away ²³	●	●	●		
Social support	MPSS, ⁸² Counselor Support ⁶⁰	●	●	●	●	●
Alcohol/substance use	WHO ASSIST ⁸³	●	●	●		

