9. Data Security. All data collected online will be maintained in encrypted, password protected computer systems. The web-based Avegen Health Machine (HM) software database will be used by the HST team to hold study data – this system uses the latest encryption data and in the U.S. meets all regulations for security and privacy of participant information. Avegen HM will also be used to collect web-based survey responses – which also use the latest security protocols for transmission and receiving online data. All data can only be accessed by logging into the online Avegen HM database and different study staff can be given different levels of access as required – all of which facilitates security, privacy. All offline data, if it exists, (which we expect there to be minimal to none) will be stored in secure locked cabinets at HST. All data will be deidentified prior to analysis and reports. Only members of the HST's research team who are in charge of follow-up and the HST site investigators will have access to the data of participants who agree to be a part of the follow-up. Their identifying information will be destroyed at the conclusion of the project by HST staff. More detail information regarding data security can be found in the Protection of Human Subjects below sections B3 and B4.

Analytic Plan

10. Outcome variables.

Aim 1 is to determine whether **CHALO! 2.0** increases HIV testing compared to control conditions, and to identify factors associated with HIV testing.

- Primary outcome: dichotomous measures (yes/no) of receipt of a verified HIV test within 6 months of randomization.
- Secondary outcomes: frequency of HIV testing within 18 months of randomization, receipt of a verified HIV test within 12 and 18 months of randomization, and receipt of a self-reported HIV test within 6 months of randomization.

Aim 2 is to determine whether **CHALO! 2.0** increases linkage-to-care (both HIV prevention through counseling and use of PrEP, and HIV treatment with antiretrovirals), and to identify factors associated with linkage to care.

- Primary outcome: dichotomous measure of linkage-to-prevention (yes/no), which will be defined as a composite of either counseling or PrEP use. We consider any counseling as prevention because of evidence that non-HIV specific counselling for MSM in India and elsewhere may confer HIV preventive behaviors directly or indirectly.⁹²⁻⁹⁴

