Stigma and Confidentiality Concerns in Terms of HIV testing: Individuals make decisions about where and how to get HIV-tested by weighing multiple perceived and actual risks/benefits of each testing strategy in the real-world, such that no single testing approach likely meets the need of majority of MSM. CHALO! 2.0 uses a pragmatic approach by linking individuals to multiple exiting testing options. The coupon will be linked to participants’ mobile numbers, and will be scanned/entered into an online system by testing staff (at HST or the private laboratory), at which time participants will immediately receive a code to provide to the tester to verify eligibility as a study participant. This will discourage sharing and use of the coupon aside from the participant, and help protect the participant’s privacy. Each coupon can only be used

once every four-weeks at the most to minimize increased harm from potential false positive due to frequent testing and to discourage sharing the coupon. All participants who get tested, will also receive an automated message with a link for a pre- and post-test counseling video, a brief, bulleted Whatsapp message covering the central points of the counseling videos, and contact information for HST's community health-worker (who can provide counseling and linkage-to-care/navigation services for both prevention and treatment, and will be blinded to participant's study condition). These steps will help ensure confidentiality of participant test results, linkage of valid test results to each participant, and ensure data integrity.

Being Outed as a sexual minority. Participation in the study could theoretically out someone if another individual saw contents on the participants Whatsapp messages about MSM health and HIV testing. However, participation in this trial is voluntary, and is not likely to pose any greater risk than already experienced by potential participants who are using gay/MSM dating apps on their mobile phones, may be having text message conversations with other gay/MSM, or accessing LGBTQ related contents from their phones. Participants will only be receiving twice weekly messages/contents – which will only be sent during daytime hours. Additionally, participants will only be contacted by online peer-counselors or healthcare workers by the method the participant indicated during enrollment.

B. ADEQUACY OF PROTECTION AGAINST RISKS.

B1. REGULATORY COMPLIANCE.

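### The Aim 2 primary outcome counts any counselling and does not exclude the counselling that is part of an HIV test, so testing at HST can by itself count as linkage to prevention

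*Combined protocol and SAP*

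**What the plan says.** All references are to the combined protocol and SAP.

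- **Outcome rule.** Section 10 defines linkage-to-prevention as a yes/no composite of counselling or PrEP use. On scope it says: "We consider any counseling as prevention because of evidence that non-HIV specific counselling for MSM in India and elsewhere" may lead to preventive behaviour, directly or indirectly.
- **Counselling at the test.** Section 2.4: "Those testing at HST via counselor or self-test will undergo standard pre- and post-test counseling", whereas "those testing at the private lab will be sent pre- and post-test counseling video links". Section 2.1 adds: "All participants who check in will also receive an automated message with a link for a pre- and post-test counseling video". Section A3 says the same of everyone tested.
- **Signs of a narrower intent.** Section 2.1 describes the HST community health worker as someone "who can provide additional counseling and linkage-to-care/navigation for prevention and treatment". Section 2.5 places linkage after the result: "All participants testing HIV-positive or HIV-negative will be offered linkage to care services". Section 8.3 lists counselling and testing as separate items: "On-site HST services include clinic use (counseling, HIV testing, PEP, and PrEP prescribing, STI testing/treatment". The exit-interview text in A2 gives safer-sex counselling as an example of prevention care.
- **Data sources.** Section A2 allows linkage to be taken from the healthcare worker log or from HST counselling and clinic records. Table 2 adds self-report.
- **Planning.** Section 13.4 expects linkage of 30%, 15% and 5% at 12 months, with the 30% taken from HST's current rate in HIV-negative individuals. It expects testing of 75%, 45% and 35%, HIV-negative samples of 247, 139 and 108, and power above 90% and above 99% at two-sided alpha 0.025.

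**The concern.** The one sentence that works as a coding rule counts any counselling. Since every HST test includes counselling, applying that sentence as written makes an HST test a linkage event. A private-lab test is not one unless the video links count, which is also unstated; a private-lab tester can still be linked through PrEP or separate counselling. Two men who do nothing beyond testing could therefore be classified differently because of where they tested.

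At stake is what the Aim 2 primary comparison measures. If test-visit counselling is included, the outcome mixes movement into prevention care with the Aim 1 outcome and the choice of test site. The secondary analysis of counselling alone has the same ambiguity; only the PrEP component is free of it. The planned exploration of whether testing strategy predicts linkage (Section 13.3) might reveal the dependence, but it would not correct the primary comparison.

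**Working it through.** **Inputs.** Section 13.4: two-sided alpha 0.025 (z = 2.241); n = 247/139/108; linkage p = 0.30/0.15/0.05; testing t = 0.75/0.45/0.35; undiagnosed HIV at most 7%. Assumed: s, the share of testers who test at HST. The only HST figure is in the Background: 10% of previously tested respondents in a pre-trial survey. It may not carry over, because the trial offers free coupons and excludes men who used HST in the past year (A1c).

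**Formula.** Power = Φ(|p1 − p2|/SE − 2.241), with unpooled SE = √[p1(1−p1)/n1 + p2(1−p2)/n2].

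**Step 1: the plan's own figure.** For 30% vs 15%, SE = √(0.21/247 + 0.1275/139) = 0.0420; 0.15/0.0420 = 3.568; Φ(1.327) = 90.8%, matching the stated >90%. For 30% vs 5% it is >99.9%. The other single-value attention-control rows of Table 4 also reproduce (70.4%, 49.8%, 21.9% against >70%, >49%, >21%). A pooled variance gives 87.1% for 30% vs 15%.

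**Step 2: do the planning rates fit the literal rule?** If every HST tester counted, linkage among people tested at HST would be near 100%, not 30%. With tested participants as the denominator, the planned 30/15/5% could arise only if at most 30%, 15% and 5% of testers used HST. The written rule and the planning rates do not sit together comfortably.

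**Step 3: denominator (a), tested HIV-negative participants only.** Suppose HST testers all count and the planned rates apply to the rest. Linkage is then s + (1 − s)p. At s = 10%: 0.10 + 0.90×0.30 = 37.0%, 0.10 + 0.90×0.15 = 23.5%, 0.10 + 0.90×0.05 = 14.5%.

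| s (same in all arms) | Linkage by arm | Power vs attention control | Power vs coupon only |
|---|---|---|---|
| 0 | 30 / 15 / 5% | 91% | >99.9% |
| 5% | 33.5 / 19.3 / 9.8% | 82% | >99.9% |
| 10% | 37.0 / 23.5 / 14.5% | 73% | 99.6% |
| 25% | 47.5 / 36.3 / 28.8% | 47% | 89% |
| 50% | 65.0 / 57.5 / 52.5% | 21% | 48% |

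Pooled variance gives 87%, 78%, 69%, 46% and 22% against attention control. Separately, 333 × 0.75 × 0.93 = 232, not 247; with 232 the unpooled fall from s = 0 to s = 10% is 90% to 72%.

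**Step 4: denominator (b), all HIV-negative randomised participants.** Assume 333 × 0.93 ≈ 310 per arm and no linkage other than test-visit counselling at HST. Linkage is then s × t. At s = 10%: 7.5% vs 4.5%, SE = 0.0190, 0.03/0.0190 = 1.576, Φ(−0.666) = 25%.

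| s | Linkage by arm | Significant vs attention control | Significant vs coupon only |
|---|---|---|---|
| 10% | 7.5 / 4.5 / 3.5% | 25% | 48% |
| 25% | 18.8 / 11.3 / 8.8% | 65% | 92% |
| 50% | 37.5 / 22.5 / 17.5% | 97% | >99.9% |

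Here the difference in testing alone produces an apparent linkage effect.

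**Step 5: does dilution also occur under (b)?** With the planned linkage among other testers added, the rate is t × [s + (1 − s)p]. At s = 0 this is 22.5% vs 6.75%; at s = 10%, 27.8% vs 10.6%. Power against attention control stays above 99.9% at s = 0, 10%, 25% and 50%. Dilution belongs to denominator (a) only.

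**The case against.** The strongest reply is that the intent can be read from context. The word any is justified by reference to counselling that is not HIV-specific, so it most naturally widens the topic rather than admitting the test encounter. Sections 2.1, 2.5, 8.3 and A2 treat linkage as something beyond the test, and the 30% rate makes little sense otherwise. This stands as evidence of intent, and a reader should not infer that the planners meant test counselling to count. It does not close the gap, because none of these passages is an outcome rule and the rule itself carries no exclusion.

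Second, staff collecting linkage outcomes are blinded to arm (Sections 7 and A1e). That limits coding that differs by arm. It does not say which events count, and uniform use of the literal rule would still tie linkage to testing at HST.

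Third, the numbers rest on assumptions. This stands. The HST share is not projected, and the step 3 illustration applies a rate taken from HST's own clients to testers elsewhere. The denominator is also open: Section 13 makes primary analyses intention to treat, Section 13.3 compares HIV-uninfected participants, and Section 13.4 sizes the comparison on those tested. A reader might infer a general loss of power to 73%, or a general bias towards CHALO! 2.0. The documents support neither: the first needs denominator (a) and a 10% share, the second needs denominator (b).

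**Conclusion.** The concern holds as a gap in the primary outcome definition. Read literally, Section 10 with Section 2.4 counts an HIV-negative HST tester as linked to prevention by testing, and this is hard to square with the 30% planning rate. That conclusion needs no assumed number.

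The size is conditional. With tested participants only and equal HST shares, the contrast with attention control is diluted: unpooled power is 91% with no HST testing, and 82% to 21% for assumed shares of 5% to 50%. With all HIV-negative randomised participants, Aim 2 partly repeats Aim 1: the planned testing rates alone give a significant result against attention control in about 25% to 97% of trials for assumed shares of 10% to 50%.

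A reader might go further and infer that every coupon tester will be counted as linked, or that private-lab testers cannot be. The documents do not support either. The first would require the video links to count, which is unstated; the second overlooks PrEP and separate counselling. Nor do they show that the data will in fact be coded the literal way. The point should be fixed before outcomes are abstracted.

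**What to change.** Amend Section 10 so that counselling counts towards linkage-to-prevention only if it is distinct from the pre- and post-test counselling, in person or by video, delivered as part of an HIV test. State that separate prevention counselling still counts, including when it takes place on the test day and when it is not HIV-specific. Apply the exclusion by type of counselling, not by date, since a date filter could remove genuine same-day work by the HST health worker.

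Use the same rule for the counselling component and for self-reported linkage. Report test-visit counselling separately by arm. Confirm that the 30/15/5% planning rates use this definition, or restate the Aim 2 power for the denominator that will be analysed.

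The cost is one sentence in the outcome definition and some coding work on HST records. The plan lists counselling and testing as separate services but does not show that the records separate test-visit counselling from other counselling. There will be fewer outcome events than under the literal rule, and the stated power may become less favourable if the 30% came from another definition.
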